15. PUBLICATION PLAN

Timely publication will be the responsibility of the principal investigator. No data should be submitted for presentation at public meetings or in abstract form without approval of the Principal Investigator and the NF Clinical Trials Consortium. Guidelines will follow the rules for publication for the NF Clinical Trials Consortium.

The results should be made public within 13 months of the end of data collection, sooner if possible. If a report is planned to be published in a peer-reviewed journal, then that initial release may be an abstract that meets the requirements of the International Committee of Medical Journal Editors. A full report of the outcomes should be made public no later than three (3) years after the end of data collection.

APPENDIX 1: NIH Consensus Conference Criteria for NF1

- Six or more café-au-lait spots (≥ 0.5 cm in prepubertal participants or ≥ 1.5 cm in post pubertal participants)
- Two or more neurofibromas of any type or one plexiform neurofibroma
- Freckling in the axilla or groin
- Optic glioma
- Two or more Lisch nodules
- A distinctive bony lesion (dysplasia of the sphenoid bone or dysplasia or thinning of long bone cortex)
- A first-degree relative with NF1

APPENDIX 2: Karnofsky and Lansky Performance Status Criteria

PERFORMANCE STATUS CRITERIA			
Karnofsky and Lansky performance scores are intended to be multiples of 10			
Karnofsky		Lansky	
Score	Description	Score	Description
• 100	Normal, no complaints, no evidence of disease	100	Fully active, normal.
90	Able to carry on normal activity, minor signs or symptoms of disease.	90	Minor restrictions in physically strenuous activity.
80	Normal activity with effort; some signs or symptoms of disease.	80	Active, but tires more quickly
70	Cares for self, unable to carry on normal activity or do active work.	70	Both greater restriction of and less time spent in play activity.
60	Required occasional assistance, but is able to care for most of his/her needs.	60	Up and around, but minimal active play; keeps busy with quieter activities.
50	Requires considerable assistance and frequent medical care.	50	Gets dressed, but lies around much of the day; no active play, able to participate in all quiet play and activities.
40	Disabled, requires special care and assistance.	40	Mostly in bed; participates in quiet activities.
30	Severely disabled, hospitalization indicated. Death not imminent.	30	In bed; needs assistance even for quiet play.
20	Very sick, hospitalization indicated. Death not imminent.	20	Often sleeping; play entirely limited to very passive activities.
10	Moribund, fatal processes progressing rapidly.	10	No play; does not get out of bed.

APPENDIX 3: Study Calendar and Required Observations (through end of therapy)

Observation	Pre-Study	Day 1 Cycle 1	Day 8 Cycle 1	Day 15 Cycle 1	Prior to subsequent cycles 2-24	End of Therapy/Off Study
History, VS: BP,HR, temperature, oxygen saturation, RR, height, weight, Physical and neurological exam ¹	x	x		x	x	x
Performance Status ¹	x	x		x	x	x
Toxicity Evaluation		x	x	x	x	x
Review Medication diary/temperature log			x	x	x	x
Concomitant Meds	x	x		x	x	x
CBC Diff ⁷	x	x	x	x	x	x
CMP/ Phosphorous ⁶	x	x			x	x
Serum or Urine Pregnancy ²	x	Prior to initiation of each cycle				
MRI-Brain with and without contrast ³ (with orbital cuts for optic pathway tumors)	x				Every 3 cycles starting with end of Cycle 3	x
MRI Spine with/without contrast ³	x				Every 3 cycles starting with end of Cycle 3	x
Ophthalmology Functional Assessments ⁴	x				Every 3 cycles starting with end of Cycle 3	x
Biology-sodium heparin green top blood samples	x		x ⁸	x	Day1 cycle 3 Day 1 cycle 6 Day 1 cycle 12	x
Quality of Life Studies	x				Cycle 6 day 1 Cycle 12 day 1	x
Tissue (with concurrent blood sample) submission if available ⁵		x	At the time surgery is performed			

1: Performance Status = Karnofsky if \geq 16 y/o or Lansky if $<$ 16 y/o; All evaluations for Day 8 and Day 15 of Cycle 1 must be done +/-48 hours, then +/-5 days for subsequent cycles.

2: Required for female patients of childbearing potential; urine or serum pregnancy test must be negative within 7 days of starting each cycle

3: Brain and/or spine MRI should be obtained depending on tumor location. MRI will be obtained at the end of cycle 3(+/-2 weeks), then every 3 cycles (+/-2 weeks), at the end of therapy/off study or at progression.

4: **Ophthalmology evaluation only for patients with optic pathway gliomas** at the end of cycle 3 (+/-2 weeks), then every 3 cycles (+/-2 weeks)

5: Tissue submission with concurrent blood sample if available 6 months prior to enrollment and at any point during protocol treatment (optional).

6: CMP: including sodium, potassium, CO₂, chloride, total protein, glucose, AST, ALT, alkaline phosphatase, albumin, calcium, total bilirubin, BUN, Creatinine including phosphorous. Labs must be completed within 14 days of cycle 1 day 1 and on day 1 +/-5 days of subsequent cycles.

7. CBC/Differential/Platelet Count: Labs must be completed within 14 days of cycle 1 day 1, +/- 48 hours of cycle 1 day 8 and day 15, and +/-5 days of subsequent cycles.

8. Collect 5-10ml of blood per sample in sodium heparin tubes for patients $<$ 8 years of age. For patients that weigh less than 10 kg, collect 2 ml on cycle 1 day 8. For patients \geq 8 years, collect 10-15 ml.

Note: MRI Brain/Spine should be obtained with and without gadolinium including pre T1, post T1, T2 and flair sequences. Both axial and either coronal or sagittal pre-post gadolinium images should be obtained. A copy of the MRI de-identified images will be submitted to the coordinating site.

APPENDIX 4: Off Therapy Observations

Observation	1-12 Months Off Therapy	13-36 Months Off Therapy	37-60 Months Off Therapy
MRI-Brain with and without contrast ^{1,2} (with orbital cuts for optic pathway tumors)	Every 3 months	Every 6 months	Every 12 months
MRI Spine with and without contrast ^{1,2}	Every 3 months	Every 6 months	Every 12 months
Ophthalmology Functional Assessments ³	Every 3 months	Every 6 months	Every 12 months
Quality of Life Studies		At month 24 ⁶	
Biology-sodium heparin green top blood samples	3 month and 12 month off therapy visit ⁵	^X ⁵	
Tissue (with concurrent blood sample) submission if available ⁴	X	X	X

1: MRI should be done +/-4 weeks for 1-12 months, +/-4 weeks for 12-36 months, +/-6 weeks for 36-60 months

2: Brain and/or spine MRI should be obtained depending on tumor location.

3: Ophthalmology evaluation only for patients with optic pathway gliomas (+/- 4 weeks for 1-12 months, +/-4 weeks for 12-36 months, +/-6 weeks for 36-60 months)

4: Tissue submission with concurrent blood sample if available at the time of progression if surgery performed (optional)

5: Biology samples should be drawn at the 3 months off therapy visit, 12 months off therapy visit and if MRI shows progression. Collect 5-10ml of blood per sample in sodium heparin tubes for patients < 8 years of age. For patients ≥ 8 years, collect 10-15 ml.

6: QOL assessment to be done at 24 months post therapy +/- 4 weeks or at progression if sooner.

Clinical evaluations including laboratory evaluations should be performed as per standard of care.

APPENDIX 5: List of Enzyme Inducing Anticonvulsants

Enzyme inducing anticonvulsants

- Carbamazepine
- Phenytoin
- Phenobarbital
- Primidone
- Oxcarbazepine
- Topiramate
- Fosphenytoin

APPENDIX 7: Optional Tumor Tissue with Concurrent Blood Sample

If a patient has surgery 6 months prior to enrollment or surgery is indicated during therapy or at the time of progression, tissue and concurrent blood sample may be obtained for banking to store in the biorepository located at the Children's Hospital of Philadelphia (CHOP), Philadelphia, PA.

1) Blood

Prior to the day of blood draw, the site will have arranged for a sample collection kit supplied by the biorepository to be shipped to the site. The Center for Data Driven Discovery in Biomedicine (D3b) at CHOP will be providing kits and labels. The kit will contain tubes and bar-coded labels (which include a specimen number) for blood collection. It will also contain shipping materials and instructions for sending collected blood samples to the biorepository, as well as a pre-paid shipping label.

Samples

- Streck tube (for plasma): ~ 2 mL.
- EDTA tube (for DNA): ~ 5 mL.
- PAXGene tube (for RNA) ~ 2.5 mL.

Tubes should be inverted at least 10 times after being drawn.

The samples will only be obtained if the total blood volume does not exceed 5 mL/kg. If not enough blood can be drawn for all tubes, the priority order for obtaining the specimens is: 1) Streck tube, 2) EDTA tube, 3) PAXGene tube.

Label the specimens with the specimen labels provided with the specimen kit.

Blood samples must be shipped (unprocessed) same day at ambient temperature to the biorepository by overnight delivery using shipping container provided by the biorepository. Samples must be shipped Monday through Thursday.

Enter the specimen numbers into the NFCTC Data Coordinating Center eDCS.

For questions about shipping, kits, tubes, etc., and to confirm the shipping address prior to sending samples, please contact: [name] ([contact]) and BioRc ([contact]).

2) Tumor Tissue

Prior to the day of surgery, the site will have arranged for a tissue sample collection kit supplied by the biorepository to be shipped to the site. The Center for Data Driven Discovery in Biomedicine (D3b) at CHOP will be providing kits and labels. The kit will contain bar-coded cryovials (which include a specimen number) for tissue collection. It will also contain shipping materials and instructions for sending collected tissue samples to the biorepository, as well as a pre-paid shipping label.

Samples

- Fresh frozen tissue: 1-2 pea sized aliquots (~ 0.3 cm³, equivalent to 0.8 cm in diameter) of excess (left over) tumor tissue. Place each aliquot in a separate cryovial and label the specimen with subject's study number. Snap freeze the aliquots in liquid nitrogen

(preferred) or dry ice and then store in a freezer at -80°C or below until they can be sent to the biorepository.

- 1 H&E stained slide cut from each submitted piece to confirm tumor is present.
- If fresh frozen tissue is unavailable, please submit processed DNA (at least 3 micrograms) and RNA (at least 400 nanograms with optimal RIN > 7) if available.

Label the specimen manifest with the subject's study number.

Fresh frozen tissue or DNA/RNA must be shipped on dry ice via overnight delivery using shipping materials provided by the biorepository. The H&E slide should be shipped at ambient temperature. Samples must be shipped Monday through Thursday.

Enter the specimen numbers into the NFCTC Data Coordinating Center eDCS.

For questions about shipping, kits, tubes, etc., and to confirm the shipping address prior to sending samples, please contact: [name] ([contact]) and BioRc ([contact]).

APPENDIX 8: Poly-ICLC Diaries

Cycle 1: Monday/Thursday Dosing

Cycle 1: Tuesday/Friday Dosing

Cycle __: Monday/Thursday Dosing

Cycle __: Tuesday/Friday Dosing

A: NF Protocol 111 Medication Diary Cycle 1

Monday/Thursday Dosing

Patient Initials _____

PID# _____

Administer Poly-ICLC as an intramuscular injection two days a week on Mondays and Thursdays. Each dose must be given at least 2 days apart. If a dose is missed, it may be given within 24 hours of when the initial dose is due. After 8 doses, do not administer any more doses until you return to clinic.

Write down the date, time, and site of administration of Poly-ICLC. For Cycle 1 record the temperature prior to each dose and 12 hours (+/- 6 hours) after each dose. After Cycle 1 temperature is only monitored on an as needed basis (if patient is not feeling well), and should be recorded if greater than 102.2° Fahrenheit (39.0° Celsius).

	Date	Time	Site of Administration	Temperature	Other Problems
Week 1 Dose 1 (Monday)				Pre-Dose Temp _____ Time _____ 12 Hour Temp _____ Time _____	
Week 1 Dose 2 (Thursday)				Pre-Dose Temp _____ Time _____ 12 Hour Temp _____ Time _____	
Week 2 Dose 1 (Monday)				Pre-Dose Temp _____ Time _____ 12 Hour Temp _____ Time _____	
Week 2 Dose 2 (Thursday)				Pre-Dose Temp _____ Time _____ 12 Hour Temp _____ Time _____	
Week 3 Dose 1 (Monday)				Pre-Dose Temp _____ Time _____ 12 Hour Temp _____ Time _____	
Week 3 Dose 2 (Thursday)				Pre-Dose Temp _____ Time _____ 12 Hour Temp _____ Time _____	
Week 4 Dose 1 (Monday)				Pre-Dose Temp _____ Time _____ 12 Hour Temp _____ Time _____	
Week 4 Dose 2 (Thursday)				Pre-Dose Temp _____ Time _____ 12 Hour Temp _____ Time _____	

B: NF Protocol 111 Medication Diary Cycle 1

Tuesday/Friday Dosing

Patient Initials _____

PID# _____

Administer Poly-ICLC as an intramuscular injection two days a week on Mondays and Thursdays. Each dose must be given at least 2 days apart. If a dose is missed, it may be given within 24 hours of when the initial dose is due. After 8 doses, do not administer any more doses until you return to clinic.

Write down the date, time, and site of administration of Poly-ICLC. For Cycle 1 record the temperature prior to each dose and 12 hours (+/- 6 hours) after each dose. After Cycle 1 temperature is only monitored on an as needed basis (if patient is not feeling well), and should be recorded if greater than 102.2° Fahrenheit (39.0° Celsius).

	Date	Time	Site of Administration	Temperature	Other Problems
Week 1 Dose 1 (Tuesday)				Pre-Dose Temp _____ Time _____ 12 Hour Temp _____ Time _____	
Week 1 Dose 2 (Friday)				Pre-Dose Temp _____ Time _____ 12 Hour Temp _____ Time _____	
Week 2 Dose 1 (Tuesday)				Pre-Dose Temp _____ Time _____ 12 Hour Temp _____ Time _____	
Week 2 Dose 2 (Friday)				Pre-Dose Temp _____ Time _____ 12 Hour Temp _____ Time _____	
Week 3 Dose 1 (Tuesday)				Pre-Dose Temp _____ Time _____ 12 Hour Temp _____ Time _____	
Week 3 Dose 2 (Friday)				Pre-Dose Temp _____ Time _____ 12 Hour Temp _____ Time _____	
Week 4 Dose 1 (Tuesday)				Pre-Dose Temp _____ Time _____ 12 Hour Temp _____ Time _____	
Week 4 Dose 2 (Friday)				Pre-Dose Temp _____ Time _____ 12 Hour Temp _____ Time _____	

C: NF Protocol 111 Medication Diary Cycle _____
Monday/Thursday Dosing

Patient Initials _____
PID# _____

Administer Poly-ICLC as an intramuscular injection two days a week on Mondays and Thursdays. Each dose must be given at least 2 days apart. If a dose is missed, it may be given within 24 hours of when the initial dose is due. After 8 doses, do not administer any more doses until you return to clinic.

Write down the date, time, and site of administration of Poly-ICLC. For Cycle 1 record the temperature prior to each dose and 12 hours (+/- 6 hours) after each dose. After Cycle 1 temperature is only monitored on an as needed basis (if patient is not feeling well), and should be recorded if greater than 102.2° Fahrenheit (39.0° Celsius).

	Date	Time	Site of Administration	Temperature (after Cycle 1 only required if patient not feeling well)	Other Problems
Week 1 Dose 1 (Monday)					
Week 1 Dose 2 (Thursday)					
Week 2 Dose 1 (Monday)					
Week 2 Dose 2 (Thursday)					
Week 3 Dose 1 (Monday)					
Week 3 Dose 2 (Thursday)					
Week 4 Dose 1 (Monday)					
Week 4 Dose 2 (Thursday)					

D: NF Protocol 111 Medication Diary Cycle _____
Tuesday/Friday Dosing

Patient Initials _____
PID# _____

Administer Poly-ICLC as an intramuscular injection two days a week on Mondays and Thursdays. Each dose must be given at least 2 days apart. If a dose is missed, it may be given within 24 hours of when the initial dose is due. After 8 doses, do not administer any more doses until you return to clinic.

Write down the date, time, and site of administration of Poly-ICLC. For Cycle 1 record the temperature prior to each dose and 12 hours (+/- 6 hours) after each dose. After Cycle 1 temperature is only monitored on an as needed basis (if patient is not feeling well), and should be recorded if greater than 102.2° Fahrenheit (39.0° Celsius).

	Date	Time	Site of Administration	Temperature (after Cycle 1 only required if patient not feeling well)	Other Problems
Week 1 Dose 1 (Tuesday)					
Week 1 Dose 2 (Friday)					
Week 2 Dose 1 (Tuesday)					
Week 2 Dose 2 (Friday)					
Week 3 Dose 1 (Tuesday)					
Week 3 Dose 2 (Friday)					
Week 4 Dose 1 (Tuesday)					
Week 4 Dose 2 (Friday)					

APPENDIX 9: Poly-ICLC Roadmap for Cycle 1

Start cycle when:

- ANC \geq 750/mm³
- Hgb \geq 8gm/dL (may transfuse PRBCs)
- Platelets \geq 75,000 (transfusion independent; > 7 days from last transfusion)
- SGPT (ALT) and SGOT (AST) = or $<$ 5x ULN

Drug	Route	Dose	Days	Comments
Poly-ICLC	IM	20mcg/kg/dose	Twice weekly on Mon/Thurs OR Tues/Friday	Injections must be given at least 48 hrs apart; a missed dose can be made up within 24 hrs Premedication with acetaminophen or ibuprofen and continued dosing every 6 hrs for 24 hrs is recommended

Cycle: 1 Height: _____ cm Weight: _____ kg BSA: _____ m²

Date Due	Date Given	Day	Poly-ICLC	Site Given	Observations
		1	_____ mcg		A, B, C, D, E, F
		4	_____ mcg		
		8	_____ mcg		B, D
		11	_____ mcg		
		15	_____ mcg		A, B, D, E
		18	_____ mcg		
		22	_____ mcg		
		25	_____ mcg		
		28			

- A. History, VS, Height, weight, PE with neuro evaluation and Performance Status
- B. CBCD
- C. CMP, Phos
- D. Biology Blood Samples: Collect 5-10ml of blood per sample in sodium heparin tubes for patients $<$ 8 years of age. For patients that weigh less than 10 kg, collect 2 ml on cycle 1 day 8. For patients \geq 8 years, collect 10-15 ml.
- E. Pregnancy Test (urine or serum BHCG) – only in females of childbearing potential (all menstruating females and any female \geq 12 years of age)
- F. QOL
- G. MRI brain with and without contrast – at the end of Cycles 3, 6, 9, 12, 15, 18, 21 and 24 (end of treatment). MRI orbits with and without contrast only for OPG.
- H. MRI spine with contrast – only if primary tumor is on the spine or clinically indicated
- I. Ophthalmology Exam – for any tumor involving the optic pathway ophthalmology exams are required at the end of Cycles 3, 6, 9, 12, 15, 18, 21, and 24 (end of treatment)

MD Signature/Date: _____

PID1/PID2: _____

APPENDIX 10: Poly-ICLC Roadmap for Cycles 2 – 24

Start each cycle when:

- ANC \geq 750/mm³, Hgb \geq 8gm/dL (may transfuse PRBCs), Platelets \geq 75,000 (transfusion independent; > 7 days from last transfusion)
- SGPT (ALT) and SGOT (AST) = or $<$ 5x ULN

Drug	Route	Dose	Days	Comments
Poly-ICLC	IM	20mcg/kg/dose	Twice weekly on Mon/Thurs OR Tues/Friday	Injections must be given at least 48 hrs apart; a missed dose can be made up within 24 hrs Premedication with acetaminophen or ibuprofen and continued dosing every 6 hrs for 24 hrs is recommended

Cycle: _____ Height: _____ cm Weight: _____ kg BSA: _____ m²

Date Due	Date Given	Day	Poly-ICLC	Site Given	Observations
		1	_____ mcg		A, B, C, D, E, F
		4	_____ mcg		
		8	_____ mcg		
		11	_____ mcg		
		15	_____ mcg		
		18	_____ mcg		
		22	_____ mcg		
		25	_____ mcg		
		28			G, H, I

- History, VS, height, weight, PE with neuro evaluation and Performance Status
- CBCD
- CMP, Phos
- Biology Blood Samples required at C3D1, C6D1, and C12 D1. 5 -10 ml of blood per sample in sodium heparin tubes for patients $<$ 8 years of age. For patients \geq 8 years, we will collect 15 ml of blood.
- Pregnancy Test (urine or serum BHCG) – only in females of childbearing potential (all menstruating females and any female \geq 12 years of age)
- QOL – required at beginning of Cycle 6 and 12 and end of therapy
- MRI brain with and without contrast – at the end of Cycles 3, 6, 9, 12, 15, 18, 21 and 24 (end of treatment)
- MRI spine with contrast – only if primary tumor is on the spine or clinically indicated
- Ophthalmology Exam – for any tumor involving the optic pathway ophthalmology exams are required at the end of Cycles 3, 6, 9, 12, 15, 18, 21, and 24 (end of treatment)

MD Signature/Date: _____

PID1/PID2: _____

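### Both Tuesday/Friday home-injection diaries (B and D) tell families to inject on Mondays and Thursdays

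*Combined protocol and SAP*

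**What the plan says.** Section 4.2 and its Table 4 offer two twice-weekly schedules, Monday/Thursday or Tuesday/Friday, to be used where possible. Injections must be at least 48 hours apart, and a missed dose may be made up within 24 hours. The roadmaps in Appendices 9 and 10 repeat both day pairs.

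Appendix 8 turns this into four diary forms, A and C for Monday/Thursday and B and D for Tuesday/Friday.

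- The form titled "B: NF Protocol 111 Medication Diary Cycle 1" carries the subheading for Tuesday/Friday dosing. Its rows alternate between the two days, for example "Week 1 Dose 2 (Friday").
- The form titled "D: NF Protocol 111 Medication Diary Cycle", for later cycles, has the same subheading and the same kind of rows, beginning "Week 1 Dose 1 (Tuesday").
- The instruction in both nevertheless reads "Administer Poly-ICLC as an intramuscular injection two days a week on Mondays and Thursdays".

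All four forms also state "Each dose must be given at least 2 days apart" and "If a dose is missed, it may be given within 24 hours of when the initial dose is due".

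**The concern.** After the supervised first dose in clinic, the remaining injections may be given at home by the participant or a parent. The instruction sentence is the only line of prose on the form that says which days to inject, and in B and D it disagrees with the heading above it and the rows below it.

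Two things could follow. A family might take one dose day from the rows and the other from the sentence, which shortens the interval between doses. The due day from which the 24-hour make-up window runs also becomes ambiguous, both for the family and for site staff deciding whether a dose was late. The diaries are reviewed at visits (section 5.2, item E), and section 14.3 uses diary recordings in the safety assessment and summarises dosing compliance, so an unclear due day carries into those descriptions.

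**Working it through.** **Consistency of the four forms (Appendix 8)**

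| Diary | Use | Heading | Instruction | Rows | Consistent? |
|---|---|---|---|---|---|
| A | Cycle 1 | Mon/Thu | Mon/Thu | Mon/Thu | Yes |
| B | Cycle 1 | Tue/Fri | Mon/Thu | Tue/Fri | No |
| C | Later cycles | Mon/Thu | Mon/Thu | Mon/Thu | Yes |
| D | Later cycles | Tue/Fri | Mon/Thu | Tue/Fri | No |

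Two of the four forms contradict themselves. Section 4.2 and both roadmaps make Tuesday/Friday a valid schedule, so the sentence is the wrong part, not the heading or rows. No other text corrects it. Because B serves cycle 1 and D serves cycles 2 to 24, a Tuesday/Friday patient has the wrong sentence in every cycle.

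**Gaps between doses if sentence and rows are mixed**

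Inputs: dose 1 on Monday (sentence) or Tuesday (row); dose 2 on Thursday (sentence) or Friday (row); one of each per week; same clock time. Gap = days apart × 24 h.

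| Within the week | Gap | Into the next week | Gap |
|---|---|---|---|
| Mon to Thu | 3 × 24 = 72 h | Thu to Mon | 4 × 24 = 96 h |
| Mon to Fri | 4 × 24 = 96 h | Thu to Tue | 5 × 24 = 120 h |
| Tue to Thu | 2 × 24 = 48 h | Fri to Mon | 3 × 24 = 72 h |
| Tue to Fri | 3 × 24 = 72 h | Fri to Tue | 4 × 24 = 96 h |

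The intended schedule alternates 72 and 96 h. The only combination that reaches the 48 h limit is Tuesday (row) then Thursday (sentence). If the Thursday dose is given earlier in the day than the Tuesday dose, the limit is breached. With an assumed difference of 2 hours the gap is 48 − 2 = 46 h.

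A 24 h gap, such as Thursday then Friday, would need an extra or made-up dose given against the form's spacing line.

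**Make-up window**

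For the first dose of the week, the rows make Tuesday the due day, so the window closes on Wednesday. The sentence makes Monday the due day, so it closes on Tuesday. A Wednesday injection is therefore a permitted make-up by the rows and out of window by the sentence.

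**The case against.** The error itself is not in dispute; the argument is over how much it matters.

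- **The 48-hour gap is not peculiar to this error.** On the correct diary A, a Monday dose made up on Tuesday and followed by the Thursday dose is also 48 h apart. On Tuesday/Friday dosing, a Tuesday dose made up on Wednesday and followed by Friday gives the same. This stands. The difference is that those cases need a missed dose, whereas on B and D the gap can arise from reading the form with nothing missed.
- **The 46-hour figure rests on an assumed injection time.** This also stands; it is an illustration.
- **A family following the rows stays within tolerance even on the sentence's reading,** because Tuesday at the same clock time is just inside 24 hours of Monday. True, but the Wednesday make-up still falls on different sides of the two readings.
- **Mixing is unlikely and guarded against.** The heading and all eight rows name the right days, the next sentence gives the spacing rule, dosing stops after eight doses until the clinic visit, families are taught by the medical team, and Appendix 3 schedules diary review on days 8 and 15 of cycle 1. These are real safeguards and hold the point at minor.
- **No clinical harm is shown from a gap slightly under 48 hours.** The background (section 2.2) regards two or three doses a week as suitable. This stands; the concern is a breach of the protocol's own minimum, not a demonstrated toxicity.

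**Conclusion.** The concern holds and is minor. Diaries B and D give a dosing instruction that conflicts with their own headings and rows, and the sentence is wrong as written. The shortest gap from mixing the two readings is 48 h, assuming one first and one second dose per week at a constant clock time; any earlier injection on the Thursday falls below the minimum. How many patients will use these forms is not given, and how often families would mix the days is unknown. Actual dates and times are recorded on the diary, so any short interval can be found afterwards. The response endpoint, sample size, error rates and analysis are not affected.

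**What to change.** In the instruction sentence of diaries B and D, change the named days to Tuesdays and Fridays. Leave A and C as they are. Reissue the two corrected forms to sites and replace any copies already dispensed.

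The edit is one phrase on each of two forms. Section 13.1 requires IRB approval of protocol changes, so the correction can go into the next amendment. Until then, sites can be asked to point out the correct days to families on the Tuesday/Friday schedule when they dispense the drug.
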